### 10.1.1. Single-Dose Plasma PK Parameters

These parameters will be computed (if estimable) from the plasma drug concentration-time data over the 12-hours following Dose 1 (Day 1, morning dose) for each study drug:

#### **Cmax**

$C_{max}$  is defined as the maximum drug or metabolite concentration observed in plasma over all PK sample concentrations. It will be obtained from the  $C_{max}$  parameter calculated by WinNonlin®. If there is no measurable concentration in the participant's PK profile, then  $C_{max}$  will be missing for that participant.  $C_{max}$  will be reported in units of ng/mL. The dose-normalized parameter  $C_{max}/Dose$  will also be reported from  $C_{max\_D}$  in WinNonlin®.

#### **Cmin**

$C_{min}$  is defined as the observed minimum concentration at the end of the dosing interval. It will be obtained from the  $C_{last}$  parameter calculated by WinNonlin®.

#### **Tmax**

Time of maximum concentration ( $T_{max}$ ) is defined as the time at which the  $C_{max}$  occurs. It will be obtained from the  $T_{max}$  parameter calculated by WinNonlin®. If there is no measurable  $C_{max}$  in the participant's PK profile, then  $T_{max}$  will be missing for that participant.  $T_{max}$  will be reported in units of h.

#### **Ke**

The terminal phase elimination rate constant ( $K_e$ ) is defined as the first-order rate constant describing the rate of decrease of drug or metabolite concentration in the terminal phase (defined as the terminal region of the PK curve where drug or metabolite concentration follows first-order elimination kinetics).  $K_e$  will be computed as the slope of a terminal region consisting of  $\geq 3$  points in the plot of log-transformed concentration data versus time.  $K_e$  will be estimated using uniform weighting.

Time points used in the estimation of  $K_e$  will be initially selected using the WinNonlin® automatic algorithm. Manually chosen time points may be used at the discretion of the PK analyst after examination of the automatically chosen points in the context of the semi-log profile to improve estimation of  $K_e$  on a case-by-case basis. The set of points chosen must contain only time points after  $T_{max}$ , include at least 3 time points, and satisfy the  $K_e$  Acceptance Criteria described above. Otherwise, the elimination rate constant and all derived parameters (apparent terminal elimination half-life [ $t_{1/2}$ ], AUC Extrapolated to Infinity [ $AUC_{0-\infty}$ ], total clearance [ $CL_T$ ], and apparent volume of distribution during terminal phase [ $V_d$ ]) will be treated as missing.

This parameter will be represented by the  $\Lambda_z$  parameter calculated by WinNonlin®.  $K_e$  will be reported in units of 1/h.

#### **t1/2**

The  $t_{1/2}$  is defined as the time required for the drug or metabolite concentration to decrease by a factor of one-half in the terminal phase. The  $t_{1/2}$  can be estimated as  $\ln(2)/K_e$ . It will be obtained from the  $HL\_{\Lambda_z}$  parameter calculated by WinNonlin®. Terminal half-life will be reported in units of h.

## AUC

$AUC_{0-\text{last}}$  is defined as the area under the concentration-time curve from dosing ( $t=0$ ) to the time of the last measured concentration.  $AUC_{0-\text{last}}$  will be estimated using the Linear Up Log Down calculation method and obtained from the  $AUC_{\text{last}}$  parameter calculated by WinNonlin®.

$AUC_{0-\infty}$  is defined as the total area under the concentration-time curve from dosing ( $t=0$ ) taken to the limit as the end time becomes arbitrarily large.  $AUC_{0-\infty}$  can be calculated by adding  $AUC_{0-\text{last}}$  to an extrapolated value equal to the last measured concentration greater than the LLOQ divided by  $Ke$ :

$$AUC_{0-\infty} = AUC_{0-\text{last}} + \frac{C_{\text{last}}}{Ke}$$

Where  $C_{\text{last}}$  is the last measured concentration  $\geq$  LLOQ.  $AUC_{0-\infty}$  will be obtained from the  $AUC_{\text{INF\_obs}}$  parameter calculated by WinNonlin®.

% $AUC_{\text{ex}}$  is defined as percentage of  $AUC_{0-\infty}$  obtained by extrapolation from time of the last measured concentration to infinity. % $AUC_{\text{ex}}$  can be calculated by dividing AUC from time of the last measured concentration to infinity by  $AUC_{0-\infty}$ :

$$\%AUC_{\text{ex}} = \frac{AUC_{0-\infty} - AUC_{0-\text{last}}}{AUC_{0-\text{inf}}},$$

If % $AUC_{\text{ex}}$  is  $>20\%$ , the estimated  $AUC_{0-\infty}$  will be excluded from statistical summaries of PK parameter estimates and downstream calculations. % $AUC_{\text{ex}}$  will be obtained from the  $AUC\%Extrap\_obs$  parameter calculated by WinNonlin®.

$AUC_{0-12}$  will be calculated as the AUC extrapolated to 12 h after dosing. This will be obtained from the WinNonlin®  $AUC0\_12$  parameter.

$AUC_{0-\text{tau}}$  will be calculated as the AUC to the end of the dosing interval. The dose-normalized parameter  $AUC_{0-\text{tau}}/\text{Dose}$  will also be reported. These parameters will be obtained from the  $AUC_{\text{tau}}$  and  $AUC_{\text{tau}}_D$  parameters in WinNonlin®, respectively.

All AUCs will be reported in units of ng\*h/mL.

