## 10. PHARMACOKINETICS

The PK Analysis Population will be used when summarizing plasma drug concentrations and will be used to conduct noncompartmental analysis (NCA). Concentrations collected that are BQL before the first measurable PK concentration above the LLOQ will be treated as 0 for plotting and for all calculations including NCA and concentration summary statistics. The first BQL concentration after the last measurable PK concentration will be imputed as  $\frac{1}{2}$  LLOQ. Otherwise, BQL concentrations will be imputed as missing. Otherwise, PK sample concentrations that are BQL will be imputed as missing.

There will be no imputation for missing concentrations. The geometric mean (GM) of concentrations will be calculated using non-missing values after imputations.

Collection of plasma samples outside of the protocol defined time window for the time point, determined by exact rather than nominal time of collection, will not result in exclusion of the sample result from NCA. Plasma samples collected out of window will be evaluated on a case-by-case basis. Results from PK plasma samples that were collected substantially outside of the protocol-defined time window will be excluded from concentration summary statistics by nominal time points and plots of mean concentration by nominal time point. Substantially out-of-window samples will be defined as twice the size of the protocol-defined windows. Plasma will be drawn at the following time points to measure the concentration of SLV213 and analyze PK parameters:

- On Day 1 MORNING DOSE: Within 30 min before the morning dose ( $t=0$ ), and at 0.5h ( $\pm 5$  min), 1h ( $\pm 5$  min), 2h ( $\pm 5$  min), 4h ( $\pm 5$  min), 6h ( $\pm 10$  min), 8h ( $\pm 10$  min), and 12h ( $\pm 15$  min) after the morning dose. (The 12h time point is the same as the pre-dose time point ( $t=0$ ) before the evening dose on Day 1)
- On Day 1 EVENING DOSE: Before ( $t=0$ ) and 12h ( $\pm 15$  min) after the evening dose. (The 12h time point is the same as the pre-dose time point before the morning dose on Day 2).
- On Days 2 to 6: Within 30 min before the morning and evening doses ( $t=0$ ) and at 12h ( $\pm 15$  min) after the morning and evening doses on each day. (The PK time point before each dose on Days 2 to 6 is the same as the 12h time point of the previously received dose.)

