## CLT

Total clearance (CLT) will be obtained from Dose/AUC∞. If % $AUC_{\text{ex}}$  is  $>20\%$ , the estimated CLT value will be excluded from statistical summaries of parameter estimates and downstream calculations. CLT will be obtained from the  $CL\_F\_obs$  parameter calculated by WinNonlin®. Clearance will be reported in units of L/h.

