### 10.1.2. Multiple-Dose Plasma PK Parameters

These parameters will be computed (if estimable) from the plasma drug concentration-time data over the 48-hour dosing interval following Dose 14 (Day 7, evening dose) for each study drug. Note that these parameter estimates assume that steady state has been achieved.

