**Linearity Index**

The Linearity Index is calculated as  $AUC_{(0-τ),ss}$  (Dose 14 [Day 7 Evening Dose]) /  $AUC_{(0-∞)}$  (Dose 1 [Day 1 Morning Dose]).

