**Table 21: Summary Statistics for SLV213 PK Parameters by Dose, 400 mg SLV213 PK Population**

[Implementation Note: PK parameters will only be summarized for participants with a measurable Ke at the specified dosing day.]

PK Parameter (Units)	N	Mean (SD)	GM (CV%)	Median	Minimum, Maximum
Day 1, Single Dose					
C max (ng/mL)	x	xx.x (xx.x)	xx.x (xx.x)	xx.x	xx, xx
C max /Dose (ng/mL/mg)	x	xx.x (xx.x)	xx.x (xx.x)	xx.x	xx, xx
C min (ng/mL)	x	xx.x (xx.x)	xx.x (xx.x)	xx.x	xx, xx
T max (h)	x	xx.x (xx.x)	xx.x (xx.x)	xx.x	xx, xx
AUC (0-t) (ng*h/mL)	x	xx.x (xx.x)	xx.x (xx.x)	xx.x	xx, xx
AUC (0-∞) (ng*h/mL)	x	xx.x (xx.x)	xx.x (xx.x)	xx.x	xx, xx
AUC (0-12) (ng*h/mL)	x	xx.x (xx.x)	xx.x (xx.x)	xx.x	xx, xx
AUC (0-last) (ng*h/mL)	x	xx.x (xx.x)	xx.x (xx.x)	xx.x	xx, xx
AUC (0-tau) (ng*h/mL)	x	xx.x (xx.x)	xx.x (xx.x)	xx.x	xx, xx
AUC (0-tau)/Dose (ng*h/mL/mg)	x	xx.x (xx.x)	xx.x (xx.x)	xx.x	xx, xx
t 1/2 (h)	x	xx.x (xx.x)	xx.x (xx.x)	xx.x	xx, xx
CL T (L/h)	x	xx.x (xx.x)	xx.x (xx.x)	xx.x	xx, xx
Ke (1/h)	x	xx.x (xx.x)	xx.x (xx.x)	xx.x	xx, xx
Vd (L)	x	xx.x (xx.x)	xx.x (xx.x)	xx.x	xx, xx
Day 7, Multiple Doses					
C max,ss (ng/mL)	x	xx.x (xx.x)	xx.x (xx.x)	xx.x	xx, xx
C max /Dose (ng/mL/mg)	x	xx.x (xx.x)	xx.x (xx.x)	xx.x	xx, xx
C min,ss (ng/mL)	x	xx.x (xx.x)	xx.x (xx.x)	xx.x	xx, xx
C avg (ng/mL)	x	xx.x (xx.x)	xx.x (xx.x)	xx.x	xx, xx
RC max a	x	xx.x (xx.x)	xx.x (xx.x)	xx.x	xx, xx
T max,ss (h)	x	xx.x (xx.x)	xx.x (xx.x)	xx.x	xx, xx
T min (h)	x	xx.x (xx.x)	xx.x (xx.x)	xx.x	xx, xx
AUC (0-48),ss (ng*h/mL)	x	xx.x (xx.x)	xx.x (xx.x)	xx.x	xx, xx
AUC (0-tau),ss (ng*h/mL)	x	xx.x (xx.x)	xx.x (xx.x)	xx.x	xx, xx
AUC (0-tau)/Dose (ng*h/mL/mg)	x	xx.x (xx.x)	xx.x (xx.x)	xx.x	xx, xx
Linearity Index b	x	xx.x (xx.x)	xx.x (xx.x)	xx.x	xx, xx

PK Parameter (Units)	N	Mean (SD)	GM (CV%)	Median	Minimum, Maximum
RAUC c	x	xx.x (xx.x)	xx.x (xx.x)	xx.x	xx, xx
t 1/2 (h)	x	xx.x (xx.x)	xx.x (xx.x)	xx.x	xx, xx
CL T (L/h)	x	xx.x (xx.x)	xx.x (xx.x)	xx.x	xx, xx
Vd,ss (L)	x	xx.x (xx.x)	xx.x (xx.x)	xx.x	xx, xx

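### The 20% extrapolation rule, applied to 12 h of Day 1 data, drops slow eliminators from the AUC(0-inf), CLT and Vd summaries and may understate AUC(0-inf) and overstate CLT

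*SAP*

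**What the plan says.** SAP 10.1.1 computes the single-dose parameters "over the 12-hours following Dose 1 (Day 1, morning dose) for each study drug". Sampling stops there because the second dose follows: "The 12h time point is the same as the pre-dose time point" for the Day 1 evening dose (SAP 10). The samples are at 0, 0.5, 1, 2, 4, 6, 8 and 12 h.

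AUC(0-inf) is AUC(0-last) plus the last quantifiable concentration divided by Ke. If the extrapolated share, %AUCex, exceeds 20%, the estimate "will be excluded from statistical summaries of PK parameter estimates and downstream calculations". The CLT paragraph says the same ("value will be excluded from statistical summaries of parameter estimates and downstream calculations"), as does the Vd paragraph. Under its own heading, "The Linearity Index is calculated as" Day 7 AUC(0-tau),ss over Day 1 AUC(0-inf), so it counts as a downstream calculation.

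A separate filter applies to the whole of Table 21: "PK parameters will only be summarized for participants with a measurable Ke at the specified dosing day". An acceptable Ke needs at least three points after Tmax and an adjusted R-squared of at least 0.90 (SAP 10.1).

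The Table 21 footnote defines N by an estimable Ke only. No shell reports how many values the 20% rule removed. Listing 10 keeps each participant's estimable values but has no %AUCex column. Protocol 9.3.7 limits these parameters only to those that can be estimated and has no 20% rule.

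**The concern.** A cut-off on extrapolated area is meant to screen out unreliable estimates. Here the window is fixed at 12 h for everyone, so %AUCex is largely a function of the participant's own half-life, and the rule sorts participants by elimination rate. Where slow elimination reflects low clearance, those removed have the larger AUC(0-inf). The summary then describes the faster eliminators under a heading that suggests the whole group, and Day 1 and Day 7 CLT may describe different people, because Day 7 rests on the "48-hour dosing interval following Dose 14 (Day 7, evening dose) for each study drug".

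The final PK data are to inform the safety monitoring committee's dose recommendation (Protocol 10.1.6). With eight active participants planned per cohort, losing even a few matters.

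**Working it through.** The plan states no figure on this point, so there is none to reproduce.

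**Inputs from the documents:** the 12 h window and sampling times, the 20% rule, linear-up log-down AUC and the Ke criteria (SAP 10 and 10.1); 8 active participants planned (SAP 5; SAP Table 4 shows 6). **Assumed, because not given:** half-life 2–8 h, the absorption rate ka, between-participant variability and assay error.

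**Step 1: half-life at which the rule bites.** With first-order elimination and immediate absorption, the share of AUC beyond 12 h is exp(−12·Ke). Setting this to 0.20 gives Ke = ln 5 / 12 = 0.134 per h, and a half-life of 12 × ln 2 / ln 5 = 5.17 h. With first-order absorption the share is (ka·exp(−12·Ke) − Ke·exp(−12·ka)) / (ka − Ke). It reaches 20% at about 4.1, 4.7, 4.9 and 5.0 h for ka = 0.5, 1, 1.5 and 3 per h. At ka = 1.5 per h it is 14% for a 4 h half-life, 21% for 5 h, 27% for 6 h and 38% for 8 h.

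**Step 2: effect on the summaries.** One-compartment oral profiles, 6,000 per scenario, were analysed with the SAP's rules under two sets of assumptions in which slow elimination goes with low clearance:

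- A: log-SD 0.3 on elimination rate and on volume, independently; ka 1.2 per h with log-SD 0.4; 15% error.
- B: CV 40% on clearance and 20% on volume; ka 1 per h with about 30% variability; 10% error.

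Geometric mean AUC(0-inf) relative to the true value:

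| Median half-life | A, with rule | A, all with acceptable Ke | B, with rule | B, all with acceptable Ke |
|---|---|---|---|---|
| 2 h | – | – | 0.95 | 0.97 |
| 3 h | 0.93 | 0.97 | 0.89 | 0.97 |
| 4 h | 0.86 | 0.95 | 0.81 | 0.95 |
| 5 h | 0.77 | 0.93 | 0.74 | 0.93 |
| 6 h | 0.68 | 0.92 | 0.66 | 0.91 |
| 8 h | – | – | 0.57 | 0.89 |

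A repeat run of both sets agreed to within about 0.02 (at 2 h under B it gave 0.96). Under A, 5.1, 3.2 and 1.6 of 8 participants remain at 4, 5 and 6 h. Under B, the rule drops 3, 15, 32, 47, 62 and 82% of those with an acceptable Ke at 2, 3, 4, 5, 6 and 8 h. CLT in those kept under B is 1.13, 1.24, 1.36 and 1.52 times the true value at 3, 4, 5 and 6 h. The shortfall that remains without the rule comes mainly from the Ke filter.

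**Step 3: change the source of variation.** If half-life varies through volume only, AUC(0-inf) in those kept is 0.98–0.99 of the true value, but Vd is 0.93 at 3 h and 0.71 at 5 h. If variation is mainly in bioavailability, AUC(0-inf) is 0.98 at 3 h and 0.88 at 5 h.

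**Step 4: Linearity Index.** Under linear kinetics the true value is 1.00. Among those kept it is about 1.02 at every half-life under B.

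**Step 5: chance of losing someone.** If 20% of participants exceed the cut-off, the probability of losing at least one is 1 − 0.8^8 = 0.83 with 8 participants and 1 − 0.8^6 = 0.74 with 6.

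**The case against.** The case for leaving the plan alone has real force:

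- **The half-life is unknown.** The single-dose results are referred to the Investigator's Brochure. If the half-life is 2–3 h, the effect is small to modest. This stands, and makes the size conditional.
- **The rule is prespecified and screens for reliability.** Values resting on a long extrapolation are individually less precise. But in a further simulation over half-lives of 2–8 h, with variation driven by clearance, volume or bioavailability, the all-acceptable-Ke geometric mean AUC(0-inf) was at least as close to the truth in every case. Its root mean squared error with 8 participants was smaller from 3 h upward. Precision is therefore not a good reason to show only the restricted summary.
- **It is partly disclosed.** Listing 10 keeps individual values, and Table 21 gives N by row, so a smaller N for AUC(0-inf) than for Cmax would be a clue. The footnote, however, attributes N to Ke alone, and %AUCex appears nowhere in the shells.
- **The consequence is limited.** The analysis is descriptive, one dose level is reported, and the halting criteria are event-based. This stands.

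A reader might infer that the plan understates exposure generally. It does not follow: the rule leaves Day 1 Cmax, AUC(0-12), AUC(0-last) and AUC(0-tau) alone, as well as Cmax,ss, AUC(0-tau),ss, AUC(0-48),ss and RAUC on Day 7. A reader might also infer that the highest-exposure participants are necessarily the ones removed. That needs slow elimination to go with high AUC; if volume drives half-life, it does not.

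**Conclusion.** The concern holds in a limited form. The rule makes inclusion in the Day 1 AUC(0-inf), CLT and Vd summaries depend on half-life, with a cut at about 4–5 h, and the planned tables do not show that it has happened.

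If the SLV213 half-life is about 4 h or longer and clearance drives its variation, the summarised AUC(0-inf) is about 14–19% low at 4 h and 23–26% low at 5 h, against about 5% and 7% if all participants with an acceptable Ke are summarised. CLT is correspondingly too high. If volume is the driver, AUC(0-inf) is nearly right and Vd is the parameter understated. At 2–3 h the AUC(0-inf) shortfall is about 4–11%, of which about 3% is present without the rule.

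It is tempting to call the Linearity Index biased as well. The calculations do not support that under linear kinetics: it loses participants and so precision. Nor do the documents show that many participants will be lost, since that depends on a half-life they do not give.

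**What to change.** In SAP 10.1.1 and Table 21:

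- Summarise AUC(0-inf), CLT, Vd and the Linearity Index for all participants with an acceptable Ke, and show the ≤20% extrapolation subset beside it.
- State the number of participants above 20% and the median %AUCex.
- Correct the N footnote so that it describes the participants actually behind each row.
- Add a %AUCex column to Listing 10.
- Name AUC(0-12) as the main Day 1 exposure measure and summarise it without the measurable-Ke restriction, which also means amending the Ke sentence in SAP 10.1.

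No data collection changes. SAP 15 allows an addendum before final data lock; after that, the change can be described and justified in the clinical study report (SAP 1). The cost is a few more table lines, and the flagged values are individually less precise. The 5–8% shortfall at 4–6 h that stays in the all-acceptable-Ke line should be acknowledged, since it comes mainly from the Ke filter.

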## CLT

Total clearance (CLT) will be obtained from Dose/AUC∞. If % $AUC_{\text{ex}}$  is  $>20\%$ , the estimated CLT value will be excluded from statistical summaries of parameter estimates and downstream calculations. CLT will be obtained from the  $CL\_F\_obs$  parameter calculated by WinNonlin®. Clearance will be reported in units of L/h.

## Vd

Apparent volume of distribution (Vd) will be calculated as (CLT)/ Ke. If % $AUC_{\text{ex}}$  is  $>20\%$ , the estimated Vd value will be excluded from statistical summaries of parameter estimates and downstream calculations. Vd will be obtained from  $Vz\_F\_obs$  calculated by WinNonlin®. Volume will be reported in units of L.

### 10.1.2. Multiple-Dose Plasma PK Parameters

These parameters will be computed (if estimable) from the plasma drug concentration-time data over the 48-hour dosing interval following Dose 14 (Day 7, evening dose) for each study drug. Note that these parameter estimates assume that steady state has been achieved.

**Cmax,ss**

$C_{max,ss}$  is the observed maximum concentration at steady state. This will be obtained from the  $Cmax$  parameter calculated by WinNonlin® for Dose 14.

**Cmin,ss**

$C_{min,ss}$  is the observed minimum concentration at the end of the dosing interval at steady state. This will be obtained from the  $Clast$  parameter calculated by WinNonlin® for Dose 14.

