8.4 Study Drug Administration

Participants will receive daily dosing Q12h (morning and evening) for 7 days, with the first dose of the study drug administered in the morning on Day 1 and the last dose in the evening of Day 7. The study product will be administered orally with at least 240 mL (8 fluid ounces) or more of tap or bottled water.

All participants are required to fast for the indicated periods before and after dosing as follows:

- Day 1, Morning dose: at least 8h before and 4h after the morning dose
- Day 1, Evening dose: at least 2h before and 1h after the evening dose

- Days 2-6, Both morning and evening doses: at least 2h before and 1h after each dose
- Day 7, Morning dose: at least 2h before and 1h after the morning dose
- Day 7, Evening dose: at least 8h before and 4h after the evening dose

Fluids will be allowed during fasting except for at least 1h before and 1h after each scheduled dose.

The meal schedule will be structured to restrict meals before and after each dose as required. Standard meals will be provided at appropriate times before and after each drug administration and the time the last meal was consumed before and after each dose on Days 1 to 7 will be recorded.

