- $AUC_{(0-tau)}$: Area under the plasma concentration - time curve from time 0 to the end of the dosing interval
- $t_{1/2}$: Terminal half-life
- CLT : Total clearance
- K_e : terminal phase elimination rate constant
- V_d : Volume of distribution
- Dose-normalized exposure parameters ($AUC_{(0-tau)}/Dose$ and $C_{max}/Dose$)

The following multiple-dose plasma PK parameters will be computed (if estimable) from the drug total concentration-time data over the 48h dosing interval following the morning dose of study drug on Day 7 in each cohort.

- $C_{max,ss}$: observed maximum concentration at steady state
- $C_{min,ss}$: observed minimum concentration at the end of the dosing interval at steady state
- C_{avg} : calculated average concentration during the dosing interval
- $T_{max,ss}$: Time of maximum concentration (C_{max}) at steady state
- T_{min} : Time to minimum concentration (C_{min})
- $AUC_{(0-48),ss}$: Area under the plasma concentration - time curve from time 0 to 48h after dosing
- $AUC_{(0-tau),ss}$: Area under the plasma concentration - time curve to the end of the dosing interval at steady state
- $t_{1/2}$: Terminal half-life (Day 7 only)
- CLT : Total clearance
- $V_{d,ss}$: Volume of distribution at steady state
- Linearity Index: $AUC_{(0-tau),ss}$ (Day 7) / $AUC_{(0-\infty)}$ (Day 1)

- RAUC: Accumulation ratio for AUC estimated as $AUC_{(0-\tau)}(\text{Day 7}) / AUC_{(0-\tau)}(\text{Day 1})$
- RC_{\max} : Accumulation ratio for C_{\max} estimated as $C_{\max}(\text{Day 7}) / C_{\max}(\text{Day 1})$.
- Dose-normalized exposure parameters ($AUC_{(0-\tau)}/\text{Dose}$ and C_{\max}/Dose)

Trough plasma concentrations of total SLV213 at 12h after each morning and evening dose from Day 1 through Day 7 will be summarized in a tabular form and presented graphically.

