	
The following multiple-dose plasma PK parameters will be computed (if estimable) from the drug total concentration-time data over the 48-hour dosing interval following the evening dose on Day 7 for each cohort.
 
 
• <math>C_{\max,ss}</math>: observed maximum concentration at steady state (ss)
 
• <math>C_{\min,ss}</math>: observed minimum concentration at the end of the dosing interval at steady state
 
• <math>C_{\text{avg}}</math>: calculated average concentration during the dosing interval
 
• <math>T_{\max,ss}</math>: Time of maximum concentration (<math>C_{\max}</math>) at steady state
 
• <math>T_{\min}</math>: Time to minimum concentration (<math>C_{\min}</math>)
 
• <math>AUC_{(0-48),ss}</math>: area under the plasma concentration - time curve from 0h (pre-dose) to 48 h after dosing at steady state
 
• <math>AUC_{(0-\tau),ss}</math>: Area under the plasma concentration - time curve to the end of the dosing interval at steady state
 
• <math>t_{1/2}</math>: Terminal half-life
 
• <math>CL_T</math>: Total clearance
 
• <math>Vd,ss</math>: Volume of distribution at steady state
 
• Linearity Index: <math>AUC_{(0-\tau),ss}</math> (Day 7) / <math>AUC_{(0-\infty)}</math> (Day 1)
 
• RAUC: Accumulation ratio for AUC estimated as <math>AUC_{(0-\tau)}</math> (Day 7) / <math>AUC_{(0-\tau)}</math> (Day 1)
 
• <math>RC_{\max}</math>: Accumulation ratio for <math>C_{\max}</math> estimated as <math>C_{\max}</math> (Day 7) / <math>C_{\max}</math> (Day 1).
 
• Dose-normalized exposure parameters (<math>AUC_{(0-\tau)}/\text{Dose}</math> and <math>C_{\max}/\text{Dose}</math>)
 
 
Calculate trough plasma concentrations of total SLV213 at 12h after each morning and evening dose from Day 1 through Day 7.

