**Tmin**

$T_{min}$  is the time to minimum concentration ( $C_{min}$ ). This will be obtained from the  $Tlast$  parameter calculated by WinNonlin® for Dose 14.

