**RAUC**

RAUC is the accumulation ratio for AUC, which is estimated as  $AUC_{(0-\tau),ss}$  (Dose 14 [Day 7 Evening Dose]) /  $AUC_{(0-\tau)}$  (Dose 1 [Day 1 Morning Dose]) where  $AUC_{(0-\tau),ss}$  (Dose 14 [Day 7 Evening Dose]) and  $AUC_{(0-\tau)}$  (Dose 1 [Day 1 Morning Dose]) are taken from the 0-12h interval on their respective days.

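### Day 7 Cmin,ss, Tmin, clearance and volume are read from outputs of a 48 h profile that do not match a 12 h dosing interval (low stakes)

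*SAP*

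**What the plan says.** Protocol Section 8.4 sets the regimen: "Participants will receive daily dosing Q12h (morning and evening) for 7 days". Sampling after the last dose (Day 7 evening, Dose 14) runs to 48 h (Protocol 8.3.4; SAP Section 10).

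SAP 10.1.2 computes the multiple-dose parameters over the "48-hour dosing interval following Dose 14 (Day 7, evening dose) for each study drug" and assumes steady state. SAP Section 3 has the same label ("over the 48-hour dosing interval following the evening dose on Day 7 for each cohort"), as does Protocol Section 3. Protocol 9.3.7 also uses it but starts from a different dose: "over the 48h dosing interval following the morning dose of study drug on Day 7 in each cohort".

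The four affected parameters in SAP 10.1.2 are:

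- **Cmin,ss**: defined as the minimum at the end of the interval, but sourced as follows: "This will be obtained from the $Clast$ parameter calculated by WinNonlin® for Dose 14".
- **Tmin**: "This will be obtained from the $Tlast$ parameter calculated by WinNonlin® for Dose 14".
- **CLT**: from CL_F_obs, with a reference to 10.1.1, where clearance is Dose/AUC-infinity.
- **Vd,ss**: from Vz_F_obs, the output that 10.1.1 uses for clearance divided by Ke.

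Elsewhere the SAP treats tau as 12 h. The two areas in the RAUC ratio "are taken from the 0-12h interval on their respective days", and AUC(0-48),ss and AUC(0-tau),ss are separate parameters in Section 3 and Table 21.

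**The concern.** On Day 1 the profile ends at 12 h, so the last sample is the end-of-interval sample, and Dose/AUC-infinity is a valid clearance after a single dose. The SAP carries the same outputs over to a Day 7 profile four times as long that follows 13 earlier doses. Neither step holds there. Nothing limits Clast or Tlast to 12 h, and the area to infinity after Dose 14 contains drug from earlier doses.

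All four parameters are named secondary endpoints. Their Day 7 rows in Table 21 would not match the SAP's own definitions. Cmin,ss could differ from the 12 h column of Table 19. Day 1 and Day 7 clearance stand under one label, so a reader could see clearance fall over the week when nothing had changed.

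**Working it through.** **1. Interval.** 7 days × 24 h / 12 h = 14 doses, which agrees with the SAP's numbering of the Day 7 evening dose as Dose 14. A 48 h interval would give 168/48 = 3.5 doses. So 48 h is the sampling period and tau is 12 h.

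**2. Assumptions.** The documents give no half-life (t½) and no LLOQ. I assume linear one-compartment kinetics, 14 doses every 12 h, the SAP's sampling times (0.5, 1, 2, 4, 6, 8, 12, 24, 36, 48 h) and t½ of 2, 4 or 6 h. The model was run with instantaneous absorption and with an absorption rate of 1/h. The formulas below are for instantaneous absorption.

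**3. Cmin,ss and Tmin.** Put the LLOQ at 1/100 of the highest sampled concentration, which is at 0.5 h. Then C12/LLOQ = 100 × 2^(-11.5/t½), and Clast/C12 = 2^(-(Tlast-12)/t½).

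| t½ | C12/LLOQ | Last quantifiable sample | Clast/C12 |
|---|---|---|---|
| 2 h | 1.86 | 12 h | 1 |
| 4 h | 13.6 | 24 h (1.70 × LLOQ) | 2^-3 = 1/8 |
| 6 h | 26.5 | 36 h (1.66 × LLOQ) | 2^-4 = 1/16 |

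An absorption rate of 1/h gives the same last column. With the LLOQ at 1/1000 of peak the ratios are 1, 1/64 and 1/64. With the LLOQ at 1/10 of peak they are 1 at 4 h and 6 h, while at 2 h the 12 h sample is itself below the LLOQ.

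**4. BQL samples.** SAP 10.1.1 defines Clast as the last concentration at or above the LLOQ. SAP Section 10 adds a rule: "The first BQL concentration after the last measurable PK concentration will be imputed as" half the LLOQ. It does not say whether that imputed value may serve as Clast.

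- Last quantifiable sample at 8 h: Clast is the 8 h value under 10.1.1. If the imputed value counts, it is half the LLOQ at 12 h, which is then the 12 h analysis value.
- Last quantifiable sample at 12 h: Clast is the 12 h value under 10.1.1, but half the LLOQ at 24 h if the imputed value counts.

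**5. Clearance and volume.** At steady state AUC(0-tau),ss = Dose/CL. After Dose 14, AUC-infinity = AUC(0-tau),ss / (1 - 2^(-12/t½)). Hence (Dose/AUC-infinity)/CL = 1 - 2^(-12/t½).

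| t½ | Instantaneous | Rate 1/h | Clearance understated by |
|---|---|---|---|
| 2 h | 1 - 1/64 = 0.984 | 0.976 | about 2% |
| 4 h | 1 - 1/8 = 0.875 | 0.853 | 13-15% |
| 6 h | 1 - 1/4 = 0.750 | 0.726 | 25-27% |

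Vz/F is this clearance divided by Ke and is low by the same factor. Dose/AUC(0-12) recovers the true clearance within 0.01% in the model.

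**6. The 20% extrapolation rule.** The share of AUC-infinity beyond 48 h is 2^(-48/t½): 0.02% at 4 h and 0.4% at 6 h. The rule never triggers on Day 7, because sampling runs to 48 h.

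**7. Limit on the half-life.** Protocol 2.3.1 reports modelling in which levels on 400 mg twice daily lie far under the 800 mg single-dose peak. The ratio of those peaks is 0.5/(1 - 2^(-12/t½)): 0.57 at 4 h, 0.67 at 6 h and 1.00 at 12 h (0.59, 0.69 and 1.04 with rate 1/h). A 12 h half-life therefore conflicts with that statement under linear kinetics and is left out.

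**The case against.** The strongest reply is that the correct quantities are already in the report.

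- **Tau is effectively settled.** The RAUC entry takes AUC(0-tau),ss itself from 0-12 h. This stands. A reader might infer that AUC(0-tau),ss, Cavg and RAUC are also computed over 48 h; the RAUC entry and the separate AUC(0-48),ss endpoint speak against that. It does not help Cmin,ss, Tmin, CLT or Vd,ss, which are tied to other outputs.
- **The trough is reported separately.** The 12 h concentration after every dose is its own secondary endpoint (Table 19, Figures 5 and 8). Table 21 is limited to participants with a measurable Ke, so it could differ from Table 19 anyway. Both stand, and they lower the stakes, but a row labelled Cmin,ss should still hold what its definition says.
- **Day 1 clearance is valid and stands in the same table.** This is true where it passes the 20% rule. The Day 1 share beyond 12 h is 2^(-12/t½) with instantaneous absorption: 12.5% at 4 h and 25% at 6 h. It passes 20% at t½ = 12/log2(5), about 5.2 h. Above that, Day 1 clearance is dropped and the understated Day 7 value is the one left.
- **Nothing is decided on these rows.** There is no hypothesis test, only the 400 mg group remains, and dosing was stopped early in four participants (SAP 6.2), so few Dose 14 profiles may exist. This stands.

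**Conclusion.** The SAP is wrong as written on these four parameters, at low stakes; it should be corrected. That Clast and Tlast are not confined to 12 h follows from the text alone. The understatement of clearance and Vz/F follows from the assumed steady state and linear kinetics. The sizes (about 2%, 13-15% and 25-27% for clearance; 1, 1/8 and 1/16 for Cmin,ss with the LLOQ at 1/100 of peak) rest on a one-compartment model and on assumed half-lives of 2, 4 and 6 h.

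Four stronger readings are tempting and not supported:

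- That clearance could be off by half. This needs a half-life near 12 h, which conflicts with Protocol 2.3.1 under linear kinetics.
- That Vd,ss is certainly too low. The direction is established for the terminal volume Vz/F. A true steady-state volume equals it only under one compartment.
- That Cmin,ss is always wrong. It is right when 12 h is the last quantifiable sample and no imputed value replaces it. When 12 h is the first BQL sample and its imputed value serves as Clast, it equals the 12 h analysis value.
- That the information is lost. Table 21 reports Day 7 AUC(0-tau)/Dose, and geometric-mean clearance in L/h = 1000 / geometric-mean AUC(0-tau)/Dose in ng·h/mL/mg.

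**What to change.** - In SAP Section 3 and 10.1.2, call the 48 h after Dose 14 a sampling period, and state tau = 12 h for every Dose 14 interval parameter. Note the same wording in Protocol Section 3 and 9.3.7, and reconcile the morning dose in 9.3.7 with the evening dose elsewhere.
- Take Cmin,ss as the 12 h concentration after Dose 14, with a stated rule when that sample is BQL, and Tmin within 0-12 h.
- Compute Day 7 CLT as Dose/AUC(0-tau),ss, and volume as that CLT divided by Ke, labelled apparent terminal volume.
- Keep the 12-48 h samples for Ke, half-life and AUC(0-48),ss.

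This needs no new samples or data, only NCA settings and wording. Vd,ss is a protocol-named endpoint, and SAP Section 15 lists no PK change. So record the new clearance formula and the relabelling there or in an addendum before data lock, otherwise in the CSR.
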